8.3.4 Safety Analysis(es)

The absolute and relative frequency of AEs in each group will be reported, including the total number of events, the total number of patients experiencing at least one event, and the frequency of events by severity and AE category.

Safety analyses will be performed on the Safety population, according to investigational product received. AEs will be regarded as 'treatment emergent' if they occur on or after the first use of investigational product at Baseline (Visit 2). In the event of a missing start date, an AE will be assumed to be 'treatment emergent' unless the end date is prior to starting treatment. In case of misallocation compared to the randomization schedule, TEAEs will be associated with the most recent investigational product received.

AE will be assessed by the investigator or medically qualified designee. AE review and coding will be in line with the Site and Safety Management Plan.

A listing of all AEs will be presented for all subjects in the Safety population with the following AE summaries (number of distinct AEs and frequency/proportion of subjects affected) presented by treatment group and overall:

- TEAEs
- TEAEs by System Organ Class (SOC) and Preferred Term (PT)
- Treatment emergent treatment related AEs by SOC and PT
- Treatment emergent treatment related serious AEs by SOC and PT

Separate listings will be presented for:

- Deaths, SAEs and any AEs leading to product or study discontinuation.
- Exposure to study product

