9.1.7 Evaluating AEs

Assessment of Intensity

The investigator or their medically qualified designee will make an assessment of intensity for each AE reported during the study and will assign it to one of the following categories:

- **Mild:** An event that is easily tolerated by the subject, causing minimal discomfort and not interfering with everyday activities.
- **Moderate:** An event that is sufficiently discomforting to interfere with normal everyday activities
- **Severe:** An event that prevents normal everyday activities.

Note: An AE assessed as 'severe' should not be confused with an SAE. 'Severe' is a category utilized for rating the intensity of an event. Both non-serious AEs and SAEs can be assessed as severe, e.g., a headache may be severe (significantly interferes with the subject's usual function) but would not be classified as serious unless it met one of the criteria for SAEs listed in [Section 9.1.2](#). An event is defined as 'serious' when it meets at least one of the pre-defined outcomes described in the definition of an SAE ([Section 9.1.2](#)), **not** when it is rated as 'severe'.

Assessment of Causality

For each AE (non-serious and serious), the investigator or their medically qualified designee **must** provide an assessment of causality in the AE section of the eCRF and on the SAE form (as appropriate, subject to classification of the AE). Causality is one of the criteria used to determine regulatory reporting requirements.

A 'reasonable possibility' of a relationship conveys there are facts (evidence) and/or arguments to suggest a causal relationship, rather than a relationship cannot be ruled out. Generally, the facts (evidence) or arguments to suggest a causal relationship should be provided in the AE/SAE report.

The investigator or their medically qualified designee will use clinical judgment to determine causality and will also consult the Investigator Brochure (IB), Safety Statement and/or Product Information, as appropriate, when making their assessment. Alternative causes, such as

Property of Haleon- Confidential

May not be used, divulged, published or otherwise disclosed without the consent of Haleon

CCI Abbreviated Clinical Protocol Template v1.0

underlying disease(s), concomitant therapy, other risk factors and the temporal relationship of the event to study product use will be considered and investigated.

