The purpose of this Statistical Analysis Plan is to describe the planned analyses and outputs to be included in the Clinical Study Report for Protocol 300217.

2 Summary of Key Protocol Information

The purpose of this trial is to demonstrate the efficacy and safety of Emergen-C Core Super Orange Powder to improve the symptoms of fatigue and quality of life (QoL). Efficacy will be demonstrated as superiority of the intervention vs. control group on the QoL assessments at 12 weeks. Safety will be demonstrated through comparison of intervention vs. control groups on incidence of treatment-emergent adverse events (TEAEs).

The study will follow a randomized, double-blind, parallel group, placebo-controlled, decentralized design with two treatment arms. After a screening period, subjects will be randomized to receive Emergen-C Core Super Orange Powder or a placebo according to a pre-specified randomization scheme.

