2.2 Study Objectives

Objectives	Endpoints
Primary Objective	Primary Endpoint
To evaluate the effect of daily supplementation with Emergen-C in improving QoL parameters as measured by the Multidimensional Fatigue Inventory (MFI) domains, compared to placebo at Week 12.	Change from Baseline at Week 12 in: 
 • General Fatigue Domain score (items 1,5,12,16) • Physical Fatigue Domain score (items 2,8,14,20) • Reduced Activity Domain score (items 3,6,10,17) • Reduced Motivation Domain score (items 4,9,15,18) • Mental Fatigue Domain score (items 7,11,13,19)
Secondary Objectives	Secondary Endpoints
Efficacy	
To evaluate the effect of daily supplementation with Emergen-C in improving QoL parameters as measured by the MFI domains, compared to placebo at Week 4 and 8.	Change from Baseline at Week 4 and 8 in: 
 • General Fatigue Domain score (items 1,5,12,16) • Physical Fatigue Domain score (items 2,8,14,20) • Reduced Activity Domain score (items 3,6,10,17) • Reduced Motivation Domain score (items 4,9,15,18)

Objectives	Endpoints
	
 • Mental Fatigue Domain score (items 7,11,13,19)
To evaluate the effect of daily supplementation with Emergen-C in improving QoL parameters as measured by the MFI individual items, compared to placebo at Week 4, Week 8 and Week 12.	
 • Change from Baseline at Week 4, Week 8 and Week 12 for each of the individual items in the MFI.
To evaluate the effect of daily supplementation with Emergen-C in improving additional QoL parameters as measured by additional QoL Questions, compared to placebo at Week 4, Week 8 and Week 12.	Change from Baseline at Week 4, Week 8 and Week 12 for: 
 • Family support (Questions 1 and 2 on additional QoL questionnaire) • Resilience (Questions 3 and 4 on additional QoL questionnaire) • Ability to relax and unwind (Questions 5 and 6 on additional QoL questionnaire)
Safety	
To monitor the safety of the study treatment with daily use for 12 weeks.	
 • The number of TEAEs [1]
Exploratory Objectives	Exploratory Endpoints

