5.7 Analysis of Safety

5.7.1 Adverse Events and Serious Adverse Events

The absolute and relative frequency of adverse events (AEs) in each group will be reported, including the total number of events, the total number of patients experiencing at least one event, and the frequency of events by severity and AE category. Safety analyses will be performed on the Safety population, according to investigational product received. AEs will be regarded as ‘treatment emergent’ if they occur on or after the first use of investigational product at baseline (visit 2). In the event of a missing start date, an AE will be assumed to be ‘treatment emergent’ unless the end date is prior to starting treatment. In case of misallocation compared to the randomization schedule, TEAEs will be associated with the most recent investigational product received.

A listing of all AEs will be presented for all subjects in the Safety population with the following AE summaries (number of distinct AEs and frequency/proportion of subjects affected) presented by treatment group and overall:

- TEAEs
- TEAEs by System Organ Class (SOC) and Preferred Term (PT)
- Treatment emergent treatment related AEs by SOC and PT
- Treatment emergent treatment related serious AEs by SOC and PT

Separate listings will be presented for:

- Deaths, Severe AEs (SAE) and any AEs leading to product or study discontinuation.
- Exposure to study product

Haleon Confidential

CCI Statistical Analysis Plan template v7.0

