14.3 Safety Data Summary Tables and Figures					
14.3.1 Displays of Adverse Events					
	Table	Treatment Emergent Adverse Events by System Organ Class and Preferred Term	Safety Population	14.3.1.1	
	Table	Treatment Related Treatment Emergent Adverse Events by System Organ Class and Preferred Term	Safety Population	14.3.1.2	
	Table	Treatment Related Treatment Emergent Serious Adverse Events by System Organ Class and Preferred Term	Safety Population	14.3.1.3	

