14.3.2 Listings of Deaths, Other Serious and Significant Adverse Events					
	Listing	Deaths	Safety Population	14.3.2.1	
	Listing	Non-Fatal Serious Adverse Events	Safety Population	14.3.2.2	

Haleon Confidential

CCI Statistical Analysis Plan template v7.0

CSR Section	TLF	Title	Population	Template	Topline
	Listing	Treatment Emergent Adverse Events Leading to Study or Product Discontinuation	Safety Population	14.3.2.3	

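### The SAP says safety will be demonstrated by comparing arms, but it plans no between-arm estimate, and its only serious-event table is limited to events judged treatment related

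*SAP*

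**What the plan says.** SAP section 2 sets the aim: "Safety will be demonstrated through comparison of intervention vs. control groups on incidence of treatment-emergent adverse events (TEAEs"). The objectives table in SAP 2.2 is more modest: "To monitor the safety of the study treatment with daily use for 12 weeks". Protocol Table 2-1 carries the same objective, with the number of TEAEs as endpoint.

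SAP 5.7.1 plans absolute and relative frequencies in each group, by severity and AE category among others. It then names four summaries by treatment group and overall: TEAEs, TEAEs by System Organ Class and Preferred Term, treatment-related TEAEs, and treatment-related serious events. Protocol 8.3.4 names the same four. Appendix 1 of the SAP carries three adverse-event tables, and the only one for serious events (Table 14.3.1.3) is titled "Treatment Related Treatment Emergent Serious Adverse Events by System Organ Class and Preferred Term".

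For the separate listings, SAP 5.7.1 has "Deaths, Severe AEs (SAE) and any AEs leading to product or study discontinuation" where Protocol 8.3.4 has "Deaths, SAEs and any AEs leading to product or study discontinuation". Protocol 9.1.7 warns: "An AE assessed as 'severe' should not be confused with an SAE". Listing 14.3.2.2 in SAP Appendix 1 is titled "Non-Fatal Serious Adverse Events".

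**The concern.** Randomisation protects the comparison of arms. Relatedness is a case-by-case judgement made afterwards. If the only table of serious events is filtered by that judgement, an imbalance made up of events judged unrelated is not shown as a count or proportion by arm. A reader would have to assemble it from listings.

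The aim in SAP section 2 also promises more than the analysis delivers. A study report that follows it could present similar-looking percentages as demonstrated safety, with no statement of how large a difference the data leave open.

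Finally, severe is a grade of intensity and serious is defined by outcome. A programmer working from the words of SAP 5.7.1 and one working from Appendix 1 would select different events for the same listing.

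**Working it through.** **The plan's own figure.** The only power statement is for the MFI endpoint (Protocol 4.1): 120 evaluable per arm, 0.5 SD, two-sided 1%, over 90% power.
- Normal approximation: Φ(0.5·√(120/2) − 2.576) = Φ(3.873 − 2.576) = Φ(1.297) ≈ 90.3%.
- Noncentral t with 238 degrees of freedom: 89.8%.
- Dropout: 240 / (1 − 0.20) = 300 randomised.

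The figure reproduces to within rounding. It concerns efficacy only. Neither document gives an expected adverse-event rate, a safety margin or a precision target, so there is no safety figure to check.

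**Where serious events appear (judged from titles, since table shells are not in the text reviewed).**

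| Output | Serious events covered | By-arm count of all serious events? |
|---|---|---|
| Table 14.3.1.1, TEAEs by SOC and PT | All treatment-emergent, mixed with non-serious | No, not separated |
| Table 14.3.1.2, related TEAEs | Related only, mixed | No |
| Table 14.3.1.3, related serious TEAEs | Related only | No |
| Listings 14.3.2.1 (deaths) and 14.3.2.2 (non-fatal serious) | All, regardless of causality | No, individual cases |
| Listing 16.2.7.1, all adverse events | All | No, individual cases |

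If no serious event is judged related, Table 14.3.1.3 is empty for every possible split between arms. The frequency by severity promised in SAP 5.7.1 has no titled table in Appendix 1.

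**What a between-arm estimate would show.** Inputs: 150 per arm (Protocol 8.1), taking everyone randomised to have at least one dose and so enter the Safety population, and the same assumed true incidence p in both arms. The 95% half-width for the risk difference is 1.96·√(2p(1 − p)/150).

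| Assumed p | Half-width (points) |
|---|---|
| 5% | 4.9 |
| 10% | 6.8 |
| 20% | 9.1 |
| 30% | 10.4 |
| 40% | 11.1 |

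For example, at p = 20%: 1.96·√(2·0.20·0.80/150) = 1.96·0.0462 = 0.0905.

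**If no event of a given type is seen in an arm of 150.** The upper limit is 1 − α^(1/150).
- α = 0.05 (one-sided 95%): 1.98%.
- α = 0.025 (two-sided 95%): 2.43%.

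The 120 per arm expected to complete is not the right denominator here, because the Safety population is everyone who took at least one dose.

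**The case against.** A reader might infer from SAP 5.7.1 that serious events of mild or moderate intensity would go unlisted. The documents do not support that. Appendix 1 plans listings of deaths and of all non-fatal serious events in the Safety population with no causality filter. SAP 5.7.1 uses the term serious correctly in its heading and in the last of its four summaries, and SAP section 6 declares no such change. The word severe is a slip.

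A reader might also infer that the SAP departed from the protocol by restricting the serious-event table. It did not: Protocol 8.3.4 has the same restriction and likewise no between-arm estimate. The gap is in both documents.

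The rest of the case for the plan is this. The operative objective is to monitor, the success criterion is efficacy only, and TEAE incidence will be shown side by side by arm. Staff making safety assessments are blinded (Protocol 7.3), and the protocol calls the intervention low risk (9.4.3). The intervals above would apply to any trial of this size. On this view, risk differences are a preference once the verb in section 2 is softened.

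Much of that stands, and it keeps the point moderate. Blinding protects the relatedness judgement from knowledge of the arm. It does not restore to the table the events that the filter removes. Side-by-side percentages meet a monitoring objective, but they do not tell the reader how much uncertainty they carry, and the SAP's own summary promises a comparison.

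**Conclusion.** The point holds as an unmatched aim and a gap in the outputs. It does not show that the safety plan as a whole is without support: what lacks support is the claim to demonstrate safety in SAP section 2. No analysis is planned that could carry it. At assumed incidences of 5 to 40%, the data would leave open differences of roughly 5 to 11 points either side of equality, and an absence of events in one arm would be compatible with a true rate of about 2%. These sizes rest on 150 dosed subjects per arm and on incidences that the documents do not give.

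Separately, all-causality serious events are never tabulated by arm, and the label in SAP 5.7.1 must be reconciled with Protocol 8.3.4 and 9.1.7 and with Listing 14.3.2.2. The label alone would be a clerical correction. The missing table and the unmatched aim bear on what the trial can conclude about safety. The primary efficacy inference is unaffected.

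**What to change.** 1. Add to SAP 5.7.1 and Appendix 1 a by-arm table of all treatment-emergent serious events regardless of causality, and name an output for the promised frequency by severity. Record the addition in SAP section 6, since Protocol 8.3.4 does not have it.
2. Report the between-arm difference, with 95% CI, in the proportion of Safety-population subjects with at least one TEAE and with at least one serious TEAE. Choose an interval method that works with zero or few events.
3. In SAP section 2, change the safety wording from demonstrating to describing, in line with the monitoring objective.
4. In SAP 5.7.1, replace the severe wording in the listing with SAEs.

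The data are already collected. The cost is a few extra outputs, some SAP wording and a more modest safety statement. SAP Appendix 2 shows that the SAP was already amended by addendum after blind data review, so a route exists. Any output added after unblinding should be labelled as such.

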5.8 Analysis of Other Variables

Not applicable.

6 Changes to the Protocol Defined Statistical Analysis Plan

Two questions outlined in the protocol section 9.10.2 were not included in this statistical analysis plan as they were not included in the study database build.

It was found that the below exploratory endpoints had been phrased differently within the database build:

- Days feeling unwell
- Days with cough and cold symptoms
- Days sick in bed

To better align with the question in the database build, the endpoints have been updated in this SAP to:

- Days feeling rundown
- Days with cold and flu symptoms
- Days of work missed

Ethnicity was also not explicitly captured within the database and has been removed from the SAP.

The definition of study product compliance was updated in the SAP to account for differences in end of treatment. In place of using the 12-week timepoint as the treatment period end, the date of last (completed) visit 4 MFI questionnaire has been used as the definition of the end of treatment. If the visit 4 MFI questionnaire was not completed, then the date of the virtual visit will be used.

7 References

- Ashbeck, Erin L., and Melanie L. Bell. 2016. 'Single Time Point Comparisons in Longitudinal Randomized Controlled Trials: Power and Bias in the Presence of Missing Data'. *BMC Medical Research Methodology* 16 (1): 43. <https://doi.org/10.1186/s12874-016-0144-0>.
- Baron, Gabriel, Philippe Ravaud, Adeline Samson, and Bruno Giraudeau. 2008. 'Missing Data in Randomized Controlled Trials of Rheumatoid Arthritis with Radiographic Outcomes: A Simulation Study'. *Arthritis and Rheumatism* 59 (1): 25–31. <https://doi.org/10.1002/art.23253>.

Haleon Confidential

CCI [REDACTED] Statistical Analysis Plan template v7.0

Page 21 of 34

- Kenward, Michael G., and James H. Roger. 1997. 'Small Sample Inference for Fixed Effects from Restricted Maximum Likelihood'. *Biometrics* 53 (3): 983–97. <https://doi.org/10.2307/2533558>.
- Rai, Sharan K, Jinoos Yazdany, Paul R Fortin, and J Antonio Aviña-Zubieta. 2015. 'Approaches for Estimating Minimal Clinically Important Differences in Systemic Lupus Erythematosus'. *Arthritis Research & Therapy* 17 (1): 143. <https://doi.org/10.1186/s13075-015-0658-6>.

Appendix 1: List of Data Displays

CSR Section	TLF	Title	Population	Template	Topline
14.1 Demographic Data Summary Tables and Figures					
	Table	Subject Disposition	All Screened Subjects	14.1.1	Yes
	Table	Demographic and Baseline Characteristics	Safety Population	14.1.3.1	Yes
	Table	Demographic and Baseline Characteristics	mITT Population	14.1.3.2	Yes
14.2 Efficacy Data Summary Tables and Figures					
	Table	Summary of Product Compliance	mITT Population	14.2.1.1.1	---
	Table	Summary of MFI Domain Scores	mITT Population	14.2.2.1.1	Yes
	Table	Summary of MFI Individual Item Scores	mITT Population	14.2.3.1.1	Yes
	Table	Summary of Quality of Life (QoL) Questions (Secondary Endpoint)	mITT Population	14.2.4.1.1	
	Table	Summary of Quality of Life (QoL) Questions (Exploratory Endpoint)	mITT Population	14.2.5.1.1	
	Table	Summary of MFI Domain Scores – Sex Subgroup	mITT Population	14.2.2.1.3	
	Table	Summary of MFI Individual Item Scores– Sex Subgroup	mITT Population	14.2.3.1.3	
	Table	Summary of QoL Questions (Secondary Endpoint) – Sex Subgroup	mITT Population	14.2.4.1.3	
	Table	Summary of MFI Domain Scores – Age Subgroup	mITT Population	14.2.2.1.5	
	Table	Summary of MFI Individual Item Scores– Age Subgroup	mITT Population	14.2.3.1.5	

Haleon Confidential

CCI Statistical Analysis Plan template v7.0

CSR Section	TLF	Title	Population	Template	Topline
	Table	Summary of QoL Questions (Secondary Endpoint) – Age Subgroup	mITT Population	14.2.4.1.5	
	Table	Statistical Analysis of Change from Baseline in Multidimensional Fatigue Inventory (MFI) Domains Over Time (MMRM)	mITT Population	14.2.2.1.2	Yes
	Table	Statistical Analysis of Change from Baseline in MFI Individual Item Scores Over Time (MMRM)	mITT Population	14.2.3.1.2	Yes
	Table	Statistical Analysis of Change from Baseline in Quality of Life (QoL) Questions (Secondary Endpoint) Over Time (MMRM)	mITT Population	14.2.4.1.2	
	Table	Statistical Analysis of Change from Baseline in Quality of Life (QoL) Questions (Exploratory Endpoint) Over Time (MMRM)	mITT Population	14.2.5.1.2	
	Table	Statistical Analysis of Change from Baseline in Multidimensional Fatigue Inventory (MFI) Domains Over Time (MMRM) – Sex Subgroup	mITT Population	14.2.2.1.4	
	Table	Statistical Analysis of Change from Baseline in MFI Individual Item Scores Over Time (MMRM) – Sex Subgroup	mITT Population	14.2.3.1.4	
	Table	Statistical Analysis of Change from Baseline in Quality of Life (QoL) Questions (Secondary Endpoint) Over Time (MMRM) – Sex Subgroup	mITT Population	14.2.4.1.4	
	Table	Statistical Analysis of Change from Baseline in Multidimensional Fatigue Inventory (MFI) Domains Over Time (MMRM) – Age Subgroup	mITT Population	14.2.2.1.6	
	Table	Statistical Analysis of Change from Baseline in MFI Individual Item Scores Over Time (MMRM) – Age Subgroup	mITT Population	14.2.3.1.6	

Haleon Confidential

CCI Statistical Analysis Plan template v7.0

CSR Section	TLF	Title	Population	Template	Topline
	Table	Statistical Analysis of Change from Baseline in Quality of Life (QoL) Questions (Secondary Endpoint) Over Time (MMRM) – Age Subgroup	mITT Population	14.2.4.1.6	
	Figure	MFI Domain Score by Visit and Study Product – General Fatigue	mITT Population	14.2.2.1.1	Yes
	Figure	MFI Domain Score by Visit and Study Product - Physical Activity	mITT Population	14.2.2.1.2	Yes
	Figure	MFI Domain Score by Visit and Study Product – Reduced Activity	mITT Population	14.2.2.1.3	Yes
	Figure	MFI Domain Score by Visit and Study Product – Reduced Motivation	mITT Population	14.2.2.1.4	Yes
	Figure	MFI Domain Score by Visit and Study Product – Mental Fatigue	mITT Population	14.2.2.1.5	Yes
14.3 Safety Data Summary Tables and Figures					
14.3.1 Displays of Adverse Events					
	Table	Treatment Emergent Adverse Events by System Organ Class and Preferred Term	Safety Population	14.3.1.1	
	Table	Treatment Related Treatment Emergent Adverse Events by System Organ Class and Preferred Term	Safety Population	14.3.1.2	
	Table	Treatment Related Treatment Emergent Serious Adverse Events by System Organ Class and Preferred Term	Safety Population	14.3.1.3	
14.3.2 Listings of Deaths, Other Serious and Significant Adverse Events					
	Listing	Deaths	Safety Population	14.3.2.1	
	Listing	Non-Fatal Serious Adverse Events	Safety Population	14.3.2.2	

Haleon Confidential

CCI Statistical Analysis Plan template v7.0

CSR Section	TLF	Title	Population	Template	Topline
	Listing	Treatment Emergent Adverse Events Leading to Study or Product Discontinuation	Safety Population	14.3.2.3	
